3.4 Early Discontinuation

All patients will be advised that they are free to withdraw from participation in this study at any time, for any reason, and without prejudice. Every reasonable attempt should be made by the investigator to keep patients in the study; however, patients must be withdrawn from the study if they withdraw consent to participate.

If a patient is discontinued early, the investigator will make every effort to complete end-of-treatment phase and follow-up phase procedures.

An electronic case report form (eCRF) should be completed for every patient who receives oliceridine, whether or not the patient completes the study. The reason for the early discontinuation should be indicated on this form. The following standard categories should be used to select a primary reason for early discontinuation:

- *Adverse event*: clinical or para-clinical events occurred that, in the medical judgment of the investigator for the best interest of the patient, are grounds for discontinuation. This includes serious and non-serious AEs regardless of relation to the IP.
- *Lack of efficacy*
- *Withdrawal of consent*: the patient desired to withdraw from further participation in the study in the absence of an investigator-determined medical need to withdraw. If the patient gave a reason for withdrawing, it should be recorded in the eCRF.
- *Investigator decision*
- *Protocol deviation*: the investigator or patient was noncompliant with study procedures or the patient did not satisfy the entry criteria for the study
- *Lost to follow-up*: the patient stopped coming for visits and study personnel were unable to contact the patient.
- *Other*: the patient was discontinued for a reason other than those listed above, such as “dosing limit”, pregnancy or termination of study by the sponsor. The reason(s) should be recorded in the eCRF.

3.5 Treatments

3.5.1 Details of Study Treatments

Information about oliceridine is provided in [Table 1](#)~~Table 1~~.

Format

Table 1: Details of the Investigational Product

	Oliceridine
IP name	TRV130 fumarate for injection
Manufacturer	Trevena, Inc.
Vial size	1, 2, 10 or 30 mL
Route	IV
Formulation	Injection
Strength(s)	1 mg/mL as free base

Oliceridine (TRV130 fumarate for injection) is formulated as a sterile aqueous solution (1 mg/mL, as free base) in a pH 7 solution containing L-histidine and mannitol.

Oliceridine is provided as a sterile, clear, colorless solution filled in 1, 2, 10, or 30 mL clear glass (type I) vials sealed with a coated rubber stopper, aluminum crimp, and flip-off plastic cap. The vial size(s) provided to the site will be determined by vial availability and the planned use at the site (e.g., 30 mL vials will only be provided to sites using the PCA regimen).

Refer to the Pharmacy and Oliceridine (TRV130) Medication Use Manual for the drug product stability, shipping, and storage conditions, and preparation instructions.

3.5.2 Oliceridine Dosing

3.5.2.1 General considerations

Oliceridine will be administered PRN via the IV route. Depending on the clinical considerations for which parenteral opioid therapy is warranted (eg, anticipated duration of therapy, clinical site/setting), a patient could receive oliceridine using clinician-administered bolus dosing or PCA dosing. A patient may receive both methods of administration.

As in current practice, patient need, analgesic efficacy, and adverse responses will guide oliceridine use. Consistent with current opioid prescribing practices for acute pain, oliceridine should not be administered on a fixed, around-the-clock dosing schedule.

The oliceridine dosing regimen should be initiated for each patient individually, taking into account the patient's severity of pain, patient response and prior analgesic treatment experience. Individually titrate oliceridine to a dose that provides adequate analgesia and minimizes AEs.

Trevena, Inc.

Protocol CP130-3003

Version 5.0

14 Sep 2016

Continually reevaluate patients receiving oliceridine to assess the maintenance of pain control and the relative incidence of AEs.

3.5.2.2 Dosing schedule

3.5.2.2.1 Clinician-administered bolus dosing

For clinician-administered bolus dosing, the oliceridine initial dose is 1 mg to 2 mg. If clinically indicated, a 1 mg supplemental dose may be administered as early as 15 minutes after the initial dose. Subsequent doses are 1 to 3 mg every 1 to 3 hours PRN based on individual patient need and previous response to oliceridine.

In settings where rapid analgesia is targeted (e.g., ED or post-anesthesia care unit (PACU)), the oliceridine initial dose is 1 mg to 3 mg. If clinically indicated, 1 mg to 3 mg supplemental doses may be administered every 5 minutes PRN. Subsequent doses are 1 to 3 mg every 1 to 3 hours PRN based on individual patient need and previous response to oliceridine.

3.5.2.2.2 PCA Regimen

For PCA dosing, the oliceridine regimen will consist of a loading dose, a demand dose, and a lockout interval without a continuous baseline infusion.

Oliceridine PCA regimen:

- Loading dose: 1.5 mg.
- Demand dose: 0.5 mg.
- Lockout interval: 6 minutes.

If clinically indicated, throughout the treatment phase, a 1 mg supplemental dose may be administered PRN, taking into account the patient's utilization of PCA demand doses, individual patient need and previous response to oliceridine.

3.5.2.3 Dosing Limit

For the current study, the dosing limit for oliceridine will be 60 mg in the first 12 hours. If a patient reaches this dosing limit within the first 12 hours, a PK sample will be obtained, the patient will early discontinue oliceridine and will be managed conventionally.

3.5.3 Drug Inventory and Accountability

The investigator must keep an accurate accounting of the number of IP units delivered to the site, dispensed to patients, returned to the investigator by site staff, returned to the sponsor, or any other disposition during and at completion of the study. The IP must be administered by an

Trevena, Inc.

Protocol CP130-3003

Version 5.0

14 Sep 2016

appropriately qualified person. The IP is to be used in accordance with the protocol by patients who are enrolled in this clinical study. Investigators should maintain records that adequately document that patients were provided the doses specified by the protocol and reconcile all IP received at the site before final disposition. At the end of the study, or as directed, all study drugs, including unused, partially used, and empty containers will be accounted for.

3.5.4 Treatment Compliance

Treatment consists of parenteral opioid therapy administered by qualified medical personnel. There is no opportunity for self-administration outside of the confines of PCA, and the study drug is not dispensed to an enrolled patient outside of the confines of the investigative site.

3.5.5 Permitted and Prohibited Prior and Concomitant Medications

Prior medications are defined as those taken before the first dose of oliceridine. Concomitant medications are defined as those taken after the first dose of oliceridine.

Concomitant non-opioid analgesics are permitted. If a concomitant parenteral or oral opioid analgesic is used during the treatment phase, oliceridine treatment will cease, and the patient will be discontinued early and will undergo the end-of-treatment phase and follow-up phase procedures as scheduled.

Unless specifically prohibited, other medications are permitted, including common treatments of opioid-related adverse effects (eg, antiemetics, antacids, stool laxatives) and medications used to treat underlying medical conditions.

As with conventional opioids, prior and concomitant use of anxiolytics, sedative-hypnotics, or other potential CNS depressants requires elevated vigilance, consistent with the Joint Commission Sentinel Event Alert for the safe use of opioids in hospitals ([The Joint Commission, 2012](#)). Similarly, the perioperative use of epidural or intrathecal opioids prior to oliceridine requires cautious administration and increased monitoring, consistent with the American Society of Anesthesiologists Task Force on Neuraxial Opioids and the American Society of Regional Anesthesia and Pain Medicine Practice Guidelines for the Prevention, Detection, and Management of Respiratory Depression Associated with Neuraxial Opioid Administration ([American Society of Anesthesiologists 2016](#)).

Supplemental oxygen will be recorded as a prior and/or concomitant medication.

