3.1.6 Follow up phase

A follow up contact will be made between 2 and 3 days after completion of the treatment phase. The contact may be conducted in person or by telephone. Concomitant medications and AEs/SAEs will be recorded.

The surgical procedure, medical diagnosis or ED diagnosis for which parenteral opioid therapy was warranted will be captured using the International Classification of Diseases, 10th Revision (ICD-10) terminology.

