3.6.2.1 Adverse Events

AEs occurring from time of informed consent to the follow-up phase will be recorded in source and will also be recorded in eCRF if the patient receives oliceridine. SAEs occurring from time of informed consent to the follow-up phase or 7 days after the last dose of oliceridine (whichever occurs later) will be recorded in source and eCRF; ongoing SAEs after this time frame will be followed until the investigator, medical monitor, and sponsor agree that the SAE is satisfactorily resolved. SAEs considered by the investigator to be related to oliceridine, regardless of the time of onset after treatment, should be reported.

AE reporting information is provided in [Section 4](#).

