6.3.2 Adverse Events

Adverse events includes any newly occurring event or previous condition that increased in severity or frequency from time of informed consent. AEs occurring from time of informed consent to the follow-up phase will be recorded in source documentation and will also be recorded in the EDC system if the patient receives oliceridine. All AEs must be recorded irrespective of whether or not they are considered medication-related. All AEs that are possibly or probably related to study medication will be followed until resolution or database lock, whichever occurs first. Changes in intensity or frequency of AEs should be recorded as separate events (i.e., a new record started).

Treatment emergent adverse events (TEAEs) are defined as AEs with onset at the time of or following the start of treatment with study medication until 7 days after the last dose of study medication or any pre-existing AEs that have worsened in severity on or after the first dose of study medication and through 7 days after the last dose of study medication.

Adverse events will be designated as treatment-emergent according to the following algorithm:

- If both the start date and start time of an AE are known, then:
- If the AE starts at any time prior to the time of the first dose on Day 1, then the AE will not be designated as treatment-emergent and hence will not be summarized.
- If the AE starts on or after the time of the first dose on Day 1 through 7 days after the last dose, then the AE will be designated as treatment-emergent.
- If only the start date of an AE is known and the start time of the AE is unknown, then:
- If the AE starts on Day 0, then the AE will not be designated as treatment-emergent and hence will not be summarized.

Client: Trevena, Inc.
 Version #: 1.0
 Version Date: 20Dec2016

Protocol/CIP #: CP130-3003

- If the AE starts on Days 1 through 7 days after the last dose, then the AE will be designated as treatment-emergent.

All AEs will be assessed on two descriptive parameters: intensity and relationship to the study medication:

- Intensity refers to the severity of an event and its impact on a patient's functioning. The following categories will be used to classify intensity:

Mild	Awareness of sign or symptom, but easily tolerated
Moderate	Discomfort enough to cause interference with usual activity
Severe	Incapacitating with inability to work or perform usual activity

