8.6.3. Adverse Events

The MedDRA version 19.0 will be used to classify all verbatim AE terms with respect to SOC and PT. Summaries will include only TEAEs and will be summarized for the Safety Analysis Set for each cumulative dose group and for all groups combined.

An overall summary of TEAEs will be performed with the following categories: any TEAE, serious TEAEs, TEAEs with the outcome of fatal, and TEAEs leading to early discontinuation. Severity rating and relationship to study medication categories will also be summarized. The summary will include unique patient counts and percentages based on the number of patients in the cumulative dose group, and the total event count. Overall summary of TEAEs will be repeated by sex, age grouping 1, age grouping 2, race, median baseline NPRS score, BMI, CYP2D6 metabolizer status and initial setting subgroups.

The number and percentage of patients with TEAEs for each cumulative dose group and overall will also be displayed by SOC and PT and will be repeated by BMI and CYP2D6 metabolizer status subgroups. These 3 summary tables will also be repeated for serious TEAEs and TEAEs leading to early discontinuation.

TEAEs will also be summarized by PT only. This summary table will be repeated by BMI and CYP2D6 metabolizer status subgroups.

TEAEs, serious TEAEs and TEAEs resulting in early discontinuation will be summarized by cumulative dose and cumulative time based on the time point intervals defined in section 6.2.4. TEAEs by cumulative dose and cumulative time based on the time point intervals will also be summarized by PTs.

A summary of most common TEAEs will be presented, where PTs occurring in at least 5% of the all treated patients group will be included. Summaries will be sorted by PT in descending frequency in the all treated patients column.

Summaries of TEAEs by maximum severity (mild, moderate, or severe) will be performed by SOC and PT. Patients with missing severities will be counted as severe. Summaries of TEAEs by maximum relationship will be performed by SOC and PT. Patients with missing relationship will be counted as probably related.

The denominator for percentages will be the number of patient within the cumulative dose group for the Safety Analysis Set. The total number of events will be presented

Client: Trevena, Inc.
Version #: 1.0
Version Date: 20Dec2016

Protocol/CIP #: CP130-3003

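### The TEAE tables do not separate events that begin after a replacement opioid has started, so AE incidence by oliceridine dose group can include another drug's events, to an unknown extent

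*Protocol*

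**What the plan says.** Two rules move a patient from oliceridine to other analgesia. Protocol 3.5.5 says "If a concomitant parenteral or oral opioid analgesic is used during the treatment phase, oliceridine treatment will cease", and such patients still complete end-of-treatment and follow-up procedures. Protocol 3.5.2.3 says that at the dosing limit "the patient will early discontinue oliceridine and will be managed conventionally". I found nothing in either document that restricts opioids once the treatment phase is over, so ordinary completers may receive them too.

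The treatment-emergent definition ignores such a move. SAP 6.3.2 takes AEs with onset at or after the first dose "until 7 days after the last dose of study medication or any pre-existing AEs that have worsened in severity". Its algorithm tests only first- and last-dose timing: "If the AE starts on or after the time of the first dose on Day 1 through 7 days after the last dose".

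Collection is narrower than the definition for most events. Protocol 3.6.2.1 says "AEs occurring from time of informed consent to the follow-up phase will be recorded in source", and Protocol 3.1.6 says "A follow up contact will be made between 2 and 3 days after completion of the treatment phase". Only SAEs are collected to at least 7 days after the last dose.

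SAP 8.6.3 then states: "Summaries will include only TEAEs and will be summarized for the Safety Analysis Set for each cumulative dose group". The subgroups in SAP 7.7 do not include later opioid use.

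**The concern.** Safety and tolerability is the primary objective, and Protocol 1.3.1 measures it as AE incidence. Nausea, vomiting, sedation and respiratory events are also effects of whatever opioid replaces oliceridine. The phase 2 abdominoplasty results in Protocol 1.1 show how far a second opioid's profile may differ: nausea 72% and vomiting 42% on morphine, against 41-46% and 15% on oliceridine.

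An event that begins after a switch is tabulated under the patient's oliceridine dose group, just like one that began during dosing. The study has one arm, so no control group shows how many such events there are. A reader of the tables could not tell whether the mixing is trivial or material.

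**Working it through.** The plan states no AE rate, switch rate or power figure to reproduce (about 1000 patients, no formal calculation). The check has three parts.

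**1. Does any planned display split onset at the switch?**
- The TEAE algorithm (SAP 6.3.2) does not refer to other drugs.
- The tables by cumulative time (mock Tables 14.3.2.4.1 and 14.3.2.5.1) define duration as first to last oliceridine dose, which does not separate events before and after a switch.
- Concomitant medications (SAP 8.5) are summarised without a link to AE onset.
- The relationship tables rely on the investigator's rating. SAP 6.3.2 lets a possibly related event be one that concomitant therapy could have produced, and pools it with probably related. SAP 8.6.3 counts a missing rating as probably related.

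No display makes the split.

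**2. How much of the counted window lies after the last dose?** Share = w/(t + w), where t is hours of treatment (assumed) and w is hours of collection afterwards.

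| t | w = 48 h | w = 72 h | w = 168 h (SAEs) |
|---|---|---|---|
| 12 h | 48/60 = 80% | 72/84 = 86% | 168/180 = 93% |
| 24 h | 48/72 = 67% | 72/96 = 75% | 168/192 = 88% |
| 48 h | 48/96 = 50% | 72/120 = 60% | 168/216 = 78% |

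This shows only that there is room for overlap. It counts all hours after oliceridine, not hours on another opioid, and it does not enter the incidence formula below.

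**3. How much could incidence move?** Reported incidence = p + (1 - p) × s × q, where p is incidence before any switch, s the share given another opioid, and q the rate of new onset afterwards among those without the event. Baselines p come from the phase 2 table in Protocol 1.1. The documents give neither s nor q, so both are assumed. The middle rows use phase 2 rescue use (31% with the 0.1 mg regimen, 21% with 0.35 mg) as an imperfect proxy for s.

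| Case | p | s | q | Added | Reported |
|---|---|---|---|---|---|
| Few switch | 46% | 10% | 5% | 0.54 × 0.10 × 0.05 = 0.3 points | 46.3% |
| Proxy, 0.35 mg | 46% | 21% | 10-30% | 0.54 × 0.21 × q = 1.1 to 3.4 points | 47.1-49.4% |
| Proxy, 0.1 mg | 41% | 31% | 10-30% | 0.59 × 0.31 × q = 1.8 to 5.5 points | 42.8-46.5% |
| Half switch | 46% | 50% | 20% | 0.54 × 0.50 × 0.20 = 5.4 points | 51.4% |
| Most switch | 46% | 90% | 30% | 0.54 × 0.90 × 0.30 = 14.6 points | 60.6% |

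For vomiting with p = 15%, the first case gives 0.85 × 0.10 × 0.05 = 0.4 points (15.4%) and the half-switch case 0.85 × 0.50 × 0.20 = 8.5 points (23.5%).

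For scale, the 95% half-width at N = 1000 is 1.96 × √(0.46 × 0.54/1000) = 3.1 points for nausea and 1.96 × √(0.15 × 0.85/1000) = 2.2 points for vomiting. The added amount is negligible if few switch, straddles sampling error for nausea at the proxy rates, and exceeds it if half or more switch.

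One limit on p: those phase 2 arms themselves had 21-31% rescue use, of a type not stated, so 41-46% may not be a clean pre-switch rate.

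**The case against.** Counting every event after first dose regardless of cause is a standard and defensible main analysis. An event soon after a switch may still be oliceridine's. In an uncontrolled study, surgery, prior opioids and other drugs confound AEs before any switch, so a cut-off does not isolate the drug's own effect.

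The plan also has partial protection. TEAEs are shown in all four relationship categories. Vital signs, oxygen saturation and sedation scores are windowed on treatment-period data plus an end-of-treatment value (SAP 6.2.4), so those objective summaries largely escape the problem. AE and medication start times already appear in Listings 16.2.5.1 and 16.2.2.2. A cut-off brings its own difficulties: patients may switch because of an AE or poor pain relief, and unequal risk windows make crude percentages too low.

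Most of this stands. It is why the planned tables should remain primary and why the added ones must show at-risk time. It does not remove the gap. The relationship rating is a judgement whose possibly related category admits other therapy, and patient-level listings are not a summary that a reader can use.

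**Conclusion.** The gap is real and should be closed with supplementary tables. The plan pools events that begin before and after a replacement opioid and offers no summary that separates them. The size is unknown: about 0.3 points on 46% nausea if few switch, about 1 to 5.5 points at the phase 2 rescue proxy, and more if most switch. Each figure rests on assumed switch and new-onset rates.

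A reader might infer more than the documents support:
- That nausea and vomiting are mixed for a full 7 days. Non-serious AEs are recorded only to the 2-3 day contact; the full 7 days applies to SAEs.
- That reported nausea would be 44-61%. That range needs 50-90% of patients to switch with 10-30% new onset (0.41 + 0.59 × 0.5 × 0.1 = 44%; 0.46 + 0.54 × 0.9 × 0.3 = 61%), and no switch rate is documented.
- That the low cumulative-dose columns are affected most. The post-treatment window is the same in every column, the added amount depends on p, s and q, and none of these is known by column. Cumulative dose is not duration either: the rapid-bolus and PCA regimens in Protocol 3.5.2.2 allow doses to accumulate within a short course.
- That the primary endpoint is uninterpretable. It remains a valid count of all events in the window; what it lacks is a view of those before the switch.

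**What to change.** Keep the planned TEAE tables as primary. Add three supplementary tables (overall, by preferred term, and serious TEAEs) limited to onset from first dose to the earlier of the first non-study opioid given after first dose and the end of the TEAE window. Show each patient's at-risk time, or exposure-adjusted rates, because the windows are unequal and the switch may be informative. Flag post-switch events in Listing 16.2.5.1.

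Define the cut-off from recorded, not imputed, opioid start times. SAP 7.3.2 sets a missing medication start time on the first-dose date to the time of first dose; used here, that would put the cut-off at time zero and remove that patient's AEs from the table. Where the order of AE and opioid on the same day is unknown, count the AE as pre-switch.

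The cost is one derived flag, a written rule for missing times and three repeat tables. Some late oliceridine events will be left out of the supplementary tables only. Nothing changes in treatment or data collection.

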3.5.6 Drug-Drug Interactions

Both non-clinical and clinical data show that oliceridine is metabolized by both CYP3A4 and CYP2D6, with each enzyme contributing approximately 50% to the clearance of oliceridine.

Trevena, Inc.

Protocol CP130-3003

Version 5.0

14 Sep 2016

The CYP2D6 enzyme is subject to significant genetic polymorphism which may affect the clearance of drugs metabolized by CYP2D6. For example, about 7%-10% of the Caucasian population may have low functional levels of CYP2D6 in the liver and are classified as “poor metabolizers”. The clearance of oliceridine in subjects who are poor metabolizers of CYP2D6 substrates is reduced by approximately 50% relative to extensive metabolizers. Patients who are taking concomitant medications known to inhibit the CYP2D6 enzyme (eg, paroxetine, fluoxetine, quinidine, bupropion) will have a similar reduction in oliceridine clearance compared to poor metabolizers. Patients who are CYP2D6 poor metabolizers, or who are taking a concomitant drug known to inhibit the CYP2D6 enzyme, may require less frequent dosing of oliceridine. Given that oliceridine is administered PRN, differential dosing instructions are not required for these patients.

Patients receiving oliceridine concomitantly with a potent CYP3A4 inhibitor (eg, clarithromycin, indinavir, itraconazole, ritonavir, lopinavir/ritonavir, mibefradil, nefazodone, nelfinavir, posaconazole, saquinavir, telaprevir, telithromycin, voriconazole) will also show a reduction in clearance of oliceridine of about 50%. These patients may require less frequent dosing of oliceridine. Given that oliceridine is administered PRN, differential dosing instructions are not required for these patients.

